Prospective Randomized Controlled Trial for Pain Relief after Office Ureteral Stent Removal

Study Protocol and Statistical Analysis Plan

NCT04112160

06/09/2020

1. Introduction and Purpose:

Ureteral stents placed after ureteroscopy (URS) for nephrolithiasis can be extremely bothersome for patients in the post-operative period. Even more troubling, a subset of patients experience debilitating renal colic for hours after the stent is removed despite use of narcotic analgesics. The purpose of this study is to determine if the use of pre-emptive ketorolac will prevent or reduce the acute pain experienced by some patients after stent removal.

2. Background:

Nephrolithiasis is a prevalent disease in the United States increasing to nearly 9% in the last decade.[1] Recently, there has been increasing attention focused on improving health-related quality of life (HRQOL) for patients with nephrolithiasis.[2] While randomized controlled trials (RCTs) are limited in this area, HRQOL is diminished in patients undergoing surgical intervention for nephrolithiasis, especially for those in whom ureteral stents were placed.[3] There are a multitude of studies focusing on reducing pain while the stent is indwelling, including the use of alpha blockers, anticholinergics, and narcotics.[4, 5] However, acute pain can occur for 1-24 hours after the indwelling stent is removed, substantially reducing quality of life. In our own quality improvement project at UT Southwestern we attempted to quantify quality of life metrics after URS and found that 57% of patients (12 of 21) reported experiencing renal colic after stent removal at home. Two of those patients went to the emergency department (ED) for severe pain right after stent removal that required intravenous medications.

Ketorolac is a safely and commonly used non-steroidal anti-inflammatory (NSAID) medication for acute renal colic.[6, 7] Ketorolac has also been uniquely formulated into intravesical instillations and indwelling ureteral stents for pain relief in the the post-operative period after URS. An RCT evaluated a ketorolac-loaded ureteral stent which helped reduce pain medication use in younger male patients between post-operative days 2-4.[8] No difference in pain scores after day 4 or in the number of interventions for pain were noted. In another study evaluating intravesical ketorolac instillation after stent placement showed benefit in the very early post-operative period (1 hour).[9] As ureteral stents are usually left indwelling for at least 1 week, an additional measure aimed at pain prevention is likely necessary after the acute benefits of ketorolac have worn off.

We propose an intervention by which ketorolac is administered intramuscularly immediately prior to office stent removal, effectively antagonizing pain receptors so that patients feel relief during and for at least 6 hours after removal, a time period that we have determined from our quality improvement project as the most likely time frame for patients to return to the ED. Furthermore, in regard to the recent focus of reducing opioid use, ketorolac injection will likely decrease or obviate the need for any narcotics after stent removal.

3. Concise Summary of Project:

This is a prospective randomized double-blind controlled trial assessing the benefits of intramuscular ketorolac before office ureteral stent removal. Patients who are undergoing cystoscopy with ureteral stent removal at the University of Texas Southwestern Medical Center and have no contraindications to receiving ketorolac will be eligible. Patients will be randomized to receive either a 1 mL injection of ketorolac tromethamine or 1 mL injection of normal saline (0.9%) as the control arm. Ketorolac is a member of the pyrrolo-pyrrole group of NSAIDs. The

mechanism of action of ketorolac, like that of other NSAIDs, is not completely understood but may be related to prostaglandin synthetase inhibition. The peak analgesic effect occurs within 2-3 hours. If no contraindications exist, ketorolac can be safely given to patients of any age in the 30 mg intramuscular formulation if given as a one time dose according to the package insert (http://www.sagentpharma.com/wp-content/uploads/2016/01/Ketorolac_-PI.pdf). It is supplied in a single-dose vial which contains either 30 mg per mL or 60 mg per 2 mL. Packages come with 25 vials per carton which costs around \$22 from the Aston pharmacy. It is recommended to store ketorolac at room temperature (20-25°C) and to protect from light until time of use. Unused portions should be discarded.

Normal saline contains 0.9% of NaCl in each mL (<https://dailymed.nlm.nih.gov/dailymed/drugInfo.cfm?setid=f2a98378-9678-4738-9670-fc7a215c0606>). Like ketorolac, it is a clear solution and given that there are no major side effects of normal saline it is a good control for our study. It is packaged in a single dose vial that contains 100 mL. It is preservative free and stored at room temperature (20-25°C). Local pain at the injection site may occur, temporarily.

4. Randomization:

After meeting inclusion procedure, patients were randomized into either the control or treatment arm. A computer-based random sequence generator was used for randomization. The allocation sequence was kept by a research nurse and concealed from the investigators and providers involved in the study. Statistical analysis was performed by a blinded investigator. Allocation was revealed after conclusion of the study.

5. Inclusion and Exclusion Criteria:

Adult patients between 18 and 80 years of age who have undergone ureteroscopy for nephrolithiasis by 2 fellowship trained surgeons (JA, MP) and placement of indwelling double-J ureteral stent(s) with or without tether at a single institution were included. Patients were required to have their stent removed in our ambulatory urology clinic. Patients were excluded if they had an absolute or relative contraindications to ketorolac. Patients with an eGFR <50, any active or history of peptic ulcer disease or gastrointestinal bleeding, bleeding disorder, suspected or confirmed cerebrovascular bleeding, hemorrhagic diathesis, incomplete hemostasis, concurrent use of warfarin or heparin, allergic reaction to NSAIDs, concurrent use of aspirin or other NSAIDs, pregnancy, recent myocardial infarction were excluded. If patients had evidence of acute renal failure at the time of stent placement, a basic metabolic profile was checked prior to the stent removal to ensure eligibility and safety for the study.

6. Medication Administration and Procedure:

Patients randomized to the treatment arm were given 30mg in 1mL intramuscular injection of ketorolac tromethamine immediately prior to removal of the ureteral stent in the ambulatory urology setting. Patients in the control arm were given a 1 mL intramuscular injection of 0.9% normal saline prior to stent removal. Medication to be injected was drawn up on the morning of stent removal by the research nurse in charge of the randomization sequence. Injections were performed by a different qualified registered nurse who was blinded to the medication. Stents were removed by the nurse if they were on a tether or via cystoscopy with the use of viscous

lidocaine instilled into the urethra. Patients in both arms were extensively counseled on expectations and symptoms to look for after stent removal.

7. Data Collection:

Patient demographical and surgical information was collected prospectively by a blinded investigator. Patients were then be contacted via telephone at 24 hours and 7 days following stent removal. Visual analog pain (VAS) scale, renal colic symptoms, need for narcotic medications, and instance of an unplanned pain-related clinical encounter, surgical interventions, and missed work were recorded. Unplanned pain-related clinical encounters were either ED visits or an unplanned ambulatory encounter with the urology clinic.

8. Statistical Analysis:

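### Narcotic use at stent removal is neither an exclusion nor a named baseline item, so the post-removal narcotic outcome cannot separate new from continuing use

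*Combined protocol and SAP*

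**What the plan says.** - **Eligibility (Section 5).** The general rule is "Patients were excluded if they had an absolute or relative contraindications to ketorolac". The concurrent drugs listed are anticoagulants ("concurrent use of warfarin or heparin, allergic reaction to NSAIDs") and certain analgesics ("concurrent use of aspirin or other NSAIDs, pregnancy, recent myocardial infarction were excluded"). Narcotics are not on the list.
- **Baseline data (Section 7).** "Patient demographical and surgical information was collected prospectively by a blinded investigator". No analgesic item is named.
- **Outcomes (Section 7).** Telephone contacts at 24 hours and 7 days after removal record "Visual analog pain (VAS) scale, renal colic symptoms, need for narcotic medications, and instance of an unplanned pain-related clinical encounter", together with surgical interventions and missed work. The item "need for narcotic medications" is not defined further.
- **Analysis (Section 8).** Categorical variables get a chi-square or Fisher's exact test, two-sided at 0.05. No stratification or covariate is mentioned.
- **Expectation (Section 2).** The authors predict that "ketorolac injection will likely decrease or obviate the need for any narcotics after stent removal".

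**The concern.** Every participant has had ureteroscopy with a stent placed, and Section 2 says stents usually stay in for at least a week. It is foreseeable that some patients will still be taking a narcotic on the day of removal. Section 2 also lists narcotics among the measures studied for "reducing pain while the stent is indwelling, including the use of alpha blockers, anticholinergics, and narcotics".

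At the 24-hour call, a patient finishing an earlier prescription and a patient who started a narcotic for new colic can give the same answer. The plan collects nothing that would tell them apart. If continuing users are counted as positive, they add similar numbers of positives to both arms, and the contrast shrinks. A null narcotic result could then mean no effect or dilution. A positive result could not be checked against an imbalance in prior users. This matters because lower narcotic need is one of the benefits the plan expects.

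**Working it through.** **Plan figures.** The documents give no sample size, power, effect size or rate of narcotic use, so there is no design figure to reproduce. The only event rate is 12/21 = 57.1% (stated as 57%). It concerns renal colic at home, not narcotic use.

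**Assumptions, none from the documents.** Among patients not on narcotics at removal, new need is p = 30% on saline and 15% on ketorolac. There are 120 patients per arm. A share c of each arm are continuing users, and all of them report need in both arms.

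**Formulas.** Observed rate: q = c + (1 − c)p. The absolute difference is therefore (1 − c) × 15 points. Power = Φ(d/SE − 1.96), with SE = √{[q₁(1 − q₁) + q₂(1 − q₂)]/120}.

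- c = 0: d = 0.15, SE = √[(0.2100 + 0.1275)/120] = 0.0530, power = Φ(0.87) = 81%.
- c = 10%: d = 0.135, SE = √[(0.2331 + 0.1798)/120] = 0.0587, power = Φ(0.34) = 63%.
- c = 25%: d = 0.1125, SE = √[(0.2494 + 0.2311)/120] = 0.0633, power = Φ(−0.18) = 43%.
- c = 40%: d = 0.09, SE = √[(0.2436 + 0.2499)/120] = 0.0641, power = Φ(−0.56) = 29%.

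| c | Saline | Ketorolac | Risk ratio | Power, all patients | Power, only those not on narcotics (n per arm) |
|---|---|---|---|---|---|
| 0 | 30% | 15% | 0.50 | 81% | 81% (120) |
| 10% | 37% | 23.5% | 0.64 | 63% | 76% (108) |
| 25% | 47.5% | 36.25% | 0.76 | 43% | 69% (90) |
| 40% | 58% | 49% | 0.84 | 29% | 59% (72) |

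A pooled-variance formula changes these powers by about one point. With that formula, other assumed rates show the same pattern. At 40% versus 20% with 82 per arm, power falls from 80% to 67% at c = 10% and 54% at c = 20%. At 57% versus 28.5% with 47 per arm, it falls from 81% to 71% and 60%.

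**Relaxing the last assumption.** Suppose a quarter of continuing users on ketorolac stop and none on saline do. The ketorolac rate becomes 0.75c + (1 − c) × 0.15.

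- c = 10%: 37% versus 21%, d = 0.16, SE = 0.0577, power 79%.
- c = 25%: 47.5% versus 30%, d = 0.175, SE = 0.0619, power 81%.
- c = 40%: 58% versus 39%, d = 0.19, SE = 0.0633, power 85%.

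The loss has largely or wholly gone. The all-patient analysis now beats the restricted one, which stays at 76%, 69% and 59%.

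**Stratified test.** Simulated power of a Cochran-Mantel-Haenszel test on all patients, stratified by narcotic use at injection, at c = 10%, 25% and 40% (good to about one point):

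- no continuing user stops: about 76%, 68% and 59%;
- a quarter stop on ketorolac: about 87%, 94% and 98%.

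In the first case the continuing-user stratum is all positive and contributes nothing, so the test matches the restricted analysis. In the second, the stratum adds information that the restricted analysis discards.

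**The case against.** The strongest reply is that several tempting readings go beyond the text.

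1. **A reader might infer a rule that continuing users count as needing narcotics whatever they were injected with.** No such rule is written. The outcome is undefined, and an interviewer might ask only about narcotics for pain after removal. This stands. What remains is that the plan neither defines the outcome nor names the data for separating the two groups.
2. **A reader might infer that narcotic use at removal is common.** The documents do not show it. The Section 2 sentence on narcotics with the stent in place summarizes published studies, not this clinic's patients. The Section 1 remark about colic despite narcotics concerns the hours after removal. No prevalence is given, and the problem could be negligible. At c = 2%, 31.4% versus 16.7% gives d = 0.147, SE = 0.0544 and power 77%, against 81% with no continuing users.
3. **A reader might infer bias towards one arm.** Allocation is randomized and blinded, so prior users balance in expectation. Chance imbalance is already covered by the test's error rate. What stands is that such an imbalance could not be seen or adjusted for.
4. **The large power losses are a worst case.** They need every continuing user to stay positive in both arms, while the plan predicts that ketorolac will reduce narcotic need. This stands, as the relaxed calculation shows.
5. **The outcome is one of six, and no primary is named.** Pain score and colic, which carry the stated purpose, do not share this coding problem. This limits the weight of the point without removing it.

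**Conclusion.** The point holds in a limited form. As written, the plan lets narcotic users in, names no item that would identify them, leaves the narcotic outcome undefined, and tests it unadjusted. New use therefore cannot be separated from continuing use.

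The consequence is possible dilution and loss of power on this outcome, plus an imbalance that could not be checked. It is neither systematic bias nor an inflated type I error. The fall from about 80% power to 63%, 43% or 29% rests on assumed rates, an assumed sample size, assumed shares of continuing users, and no continuing user stopping. The true size cannot be settled from the documents. Because no primary outcome is named, neither can its weight in the main conclusion. The change is still worth making because it is cheap and, in essentially every case run, the stratified test matched or beat the unadjusted one.

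**What to change.** 1. In Section 7, add one baseline question, asked in clinic before the injection: has the patient taken any narcotic in the previous 24 hours?
2. In Section 7, define the narcotic outcome so that new and continuing use are recorded separately at each call, and report both by arm.
3. In Section 8, compare narcotic need in all randomized patients, stratified by the baseline answer, for example with a Cochran-Mantel-Haenszel test.
4. Treat an analysis restricted to patients not on narcotics at injection as supportive only. It drops randomized patients and ignores any opioid-sparing effect in continuing users, so it answers a different question.

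If patients have already been treated, prior use could be sought from clinic medication or prescription records, where available, by someone blind to arm. Otherwise the limitation should be stated beside the narcotic result.

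The cost is one extra question and a stratified test instead of a simple one. Eligibility and prescribing do not change.
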